## 10.5 Appendix 5: Future Biospecimen Research

#### Use/Analysis of DNA

- Genetic variation may impact a subject's response to IMP, susceptibility to, and severity and progression of disease. Variable response to IMP may be due to genetic determinants that impact drug absorption, distribution, metabolism, and excretion; mechanism of action of the drug; disease etiology; and/or molecular subtype of the disease being treated. Therefore, where local regulations and IRB/IEC allow, a blood sample will be collected for DNA analysis from consenting subjects.
- DNA samples will be used for research related to CVL-865 or epilepsy and related diseases. They may also be used to develop tests/assays including diagnostic tests related to CVL-865 or interventions of this drug class and epilepsy. Genetic research may consist of the analysis of one or more candidate genes or the analysis of genetic markers throughout the genome or analysis of the entire genome (as appropriate).
- There are no planned analyses of DNA samples. Analyses may be conducted if it is hypothesized that this may help further understand the clinical data.
- The samples may be analyzed as part of a multi-trial assessment of genetic factors involved in the response to CVL-865 or IMPs of this class to understand trial disease or related conditions.
- The results of genetic analyses may be reported in the CSR or in a separate trial summary.
- The sponsor will store the DNA samples in a secure storage space with adequate measures to protect confidentiality.
- The samples will be retained while research on CVL-865 or interventions of this class or epilepsy continues but no longer than 15 years or other period as per local requirements.

CYP 3A Inhibitors CYP 3A Inducers		
HIV antivirals	HIV antivirals	
Indinavir	Efavirenz	
Nelfinavir	Nevirapine	
Ritonavir	Etravirine	
Saquinavir	Miscellaneous	
Boceprevir	Barbiturates	
Lopinavir/ritonavir	Carbamazepine	
Amprenavir	Eslicarbazepine	
Atazanavir	Glucocorticoids (systemic)	
Telaprevir	Modafinil	
Darunavir/ritonavir	Oxcarbazepine d	
Fosamprenavir	Phenobarbital	
Antibiotics	Phenytoin	
Clarithromycin	Pioglitazone	
Erythromycin	Rifabutin	
Telithromycin	Rifampin	
Ciprofloxacin	St. John's wort	
Anti-infectives	Troglitazone	
Itraconazole	Bosentan	
Ketoconazole	Nafcillin	
Fluconazole	Avasimibe	
Posaconazole		
Voriconazole		
Anti-anginal therapy		
Diltiazem		
Verapamil		
Anti-cancer therapy		
Crizotinib		
Imatinib		
Miscellaneous		
Nefazodone		
Aprepitant		
Grapefruit juice a,b		
Conivaptan		
Mibefradil c		
a The effect of grapefruit juice varies widely among brands and is concentration, dose, and		

## 10.6 Appendix 6: Inducers and Inhibitors of Cytochrome P450 3A

- a The effect of grapefruit juice varies widely among brands and is concentration-, dose-, and preparation dependent. Studies have shown that it can be classified as a "strong CYP3A inhibitor" when a certain preparation was used (eg, high dose, double strength) or as a "moderate CYP3A inhibitor" when another preparation was used (eg, low dose, single strength).
- b A 2-week washout prior to dosing is required if grapefruit juice was being consumed continually.
- c Withdrawn from the United States market.
- d Doses >900 mg/day.

10.7 Append	lix 7: Abbreviations
Abbreviation	Definition
AE	Adverse event
AED	Anti-epileptic drug
AESI	Adverse event of special interest
ALT	Alanine aminotransferase
ANCOVA	Analysis of covariance
APMP	Abuse Potential Monitoring Plan
AST	Aspartate aminotransferase
BCRP	Breast cancer resistance protein
BID	Twice daily
BMI	Body mass index
BZD	Benzodiazepine
CBC	Complete blood count
CGI-I	Clinical Global Impression-Improvement
CGI-S	Clinical Global Impression-Severity of Symptoms
CI	Confidence interval
CIOMS	Council for International Organizations of Medical Sciences
CONSORT	Consolidated Standard of Reporting Trials
CSR	Clinical study report
C-SSRS	Columbia-Suicide Severity Rating Scale
СТ	Computed tomography
СҮР	Cytochrome P450
DBS	Deep brain stimulator
DNA	Deoxyribonucleic acid
DSM-5	Diagnostic and Statistical Manual of Mental Disorders, 5th Edition
ECG	Electrocardiogram
eCRF	Electronic case report form
EEG	Electroencephalogram
ESAM	Events Subject to Additional Monitoring
ET	Early Termination
EU	European Union

Abbreviation	Definition
EudraCT	European Clinical Trials Database
FAS	Full Analysis Set
GABAA	γ-aminobutyric acid type A
GCP	Good Clinical Practice
HBV	Hepatitis B virus
HCV	Hepatitis C virus
HIPAA	Health Insurance Portability and Accountability Act
HIV	Human immunodeficiency virus
HUI	Health Utilities Index
ICF	Informed Consent Form
ICH	International Council for Harmonisation
IEC	Independent Ethics Committee
ILAE	International League Against Epilepsy
IMP	Investigational medicinal product
IRB	Institutional Review Board
IRT	Interactive response technology
ITT	Intent-to-Treat
K 2 EDTA	Dipotassium ethylenediamine tetraacetic acid
LSMean	Least square mean
mCIWA-B	Modified Clinical Institute Withdrawal Assessment-Benzodiazepines
mITT	Modified Intent-to-Treat
MedDRA	Medical Dictionary for Regulatory Activities
MHI	Medication handling irregularity
MHP	Mental Health Professional
MMRM	Mixed Model for Repeated Measures
MRI	Magnetic resonance imaging
NOAEL	No observed adverse effect level
OLE	Open-label extension
PAM	Positive allosteric modulator
PD	Pharmacodynamic
PGIC	Patient's Global Impression of Change

---

Abbreviation	Definition
P-gp	P-glycoprotein
PGx	Pharmacogenomics
PK	Pharmacokinetic
QOLIE-31	Quality of Life in Epilepsy-31
QTcF	QT interval as corrected for heart rate by Fridericia's formula
RNA	Ribonucleic acid
RNS	Responsive neurostimulator
RRatio	Response ratio
SAE	Serious adverse events
SAP	Statistical Analysis Plan
SF	Screen Failures
SIF/DRF	Seizure Identification and Diagnostic Review Form
SUSAR	Suspected Unexpected Serious Adverse Reaction
TEAE	Treatment-emergent adverse event
TESC	The Epilepsy Study Consortium
ULN	Upper limit of normal range
US	United States
VNS	Vagus nerve stimulator
WBC	White blood cell
WOCBP	Women of childbearing potential

\_\_\_\_\_

# Document HistoryDocument:Date (Day-Month-Year)Version 4.030 Jun 2020Version 3.015 Nov 2019Version 2.003 Oct 2019Original Protocol Version 1.024 Jul 2019

#### **10.8** Appendix 8: Protocol Amendment History

The Protocol Amendment Summary of Changes Table for the current amendment is located directly before the Table of Contents.

#### Amendment: Protocol Version 3.0 (15 Nov 2019)

This amendment is considered to be substantial based on the criteria set forth in Article 10(a) of Directive 2001/20/EC of the European Parliament and the Council of the European Union.

**Overall Rationale for the Amendment:** To revise relevant sections of the protocol to minimize potential risk to subjects.

Section # and Name	Description of Change	Brief Rationale
Table 1 Objectives and Endpoints	Reworded secondary endpoint for TEAEs	Consistency with open-label extension protocol
Table 3 Objectives and Endpoints		
Table 2 Schedule of Assessments	Addition of time points for safety laboratory blood samples (Visits 3, 5, and 6)	Monitoring of new potential risk of bone marrow suppression and decrease in peripheral hematologic parameters

 
2.3 Benefit/Risk
 
Assessment
 
5.2 Exclusion Criteria
 
7.3 Individual Subject
 
Discontinuation
 
8.4.6.2 Hematologic
 
Abnormalities
 
	Added potential risk of bone marrow suppression and decrease in peripheral hematologic parameters Updated relevant risk minimization measures, exclusion criterion, criteria for discontinuation of IMP, and new AESI subsection	Update relevant protocol section with new potential risk of bone marrow suppression and decrease in peripheral hematologic parameters
5.2 Exclusion Criteria	Revised criterion for HIV, hepatitis B, and hepatitis C	Exclude subjects regardless of LFT results
8.3.2 Vital Sign Measurements	Reworded paragraph about blood pressure measurement	Simplification of vital signs collection procedure

Required Safety monitoring Laboratory Assessments	ble 9 Protocol- equired Safety boratory ssessments	Added chloride and bicarbona
---	---	------------------------------

Abbreviations: AESI = adverse event of special interest; HIV = human immunodeficiency virus; IMP = investigational medicinal product; WBC = white blood cell; TEAE = treatment-emergent adverse event

### Amendment: Protocol Version 2.0 (03 Oct 2019)

This amendment is considered to be substantial based on the criteria set forth in Article 10(a) of Directive 2001/20/EC of the European Parliament and the Council of the European Union.

Section # and Name	Description of Change	Brief Rationale
Title Page Section 1 Protocol Summary	Addition of the EudraCT number	EudraCT number was included based on decision to conduct trials in countries in the European Union
Sponsor signatories	Change from , MD to MD	Change in sponsor personnel
Section 1.1 Synopsis Section 1.2 Schema Section 1.3 Schedule of Assessments Section 4.1 Overall Design	Text added to indicate subjects would enter the open-label extension trial CVL-865-SZ- 002 at the end of the Maintenance Phase instead of Taper Phase; modification to duration of Treatment Phase to indicate 10 weeks for subjects who continue treatment in Trial CVL-865-SZ-002; footnote for dosing table added to clarify dosing for subjects who continue treatment in Trial CVL-865-SZ-002; footnote in Schedule of Assessments modified	In order to avoid unnecessary taper and retitration of investigational medicinal product for subjects entering Trial CVL- 865-SZ-002, the point of entry into that trial was moved to the end of the Maintenance Phase (Visit 4)
Section 1.3 Schedule of Assessments	Change to row for "blood pressure and pulse rate" to "vital sign measurements"	Change made as measurements also include body temperature and respiratory rate
Section 1.3 Schedule of Assessments	Addition of physical/neurological examination to Visit 4 assessments	Based on decision to have eligible subjects enter the open-label extension trial CVL- 865-SZ-002 at the end of the Maintenance Phase, this examination serves as baseline for the extension trial

Section # and Name	Description of Change	Brief Rationale
Section 1.3 Schedule of Assessments	Footnote regarding rescreening was modified to indicate subjects would not retain their subject number in the event they were rescreened.	Correction of inaccurate information
Section 1.3 Schedule of Assessments	Footnote regarding timing of physical/neurological examinations was modified.	Correction of inaccurate information and addition of examination at Visit 4
Section 1.3 Schedule of Assessments	Removal of language stating female subjects with exclusively same sex partners are not required to have pregnancy tests	Change made to be consistent with sponsor standard practices
Section 4.4 Definition of Completed Subject	Modified text to indicate subjects who continued into Trial CVL-865-SZ-002 were considered to have completed Trial CVL-865-SZ-001 at Visit 4.	In order to avoid unnecessary taper and re- titration of investigational medicinal product for subjects entering Trial CVL- 865-SZ-002, the point of entry into that trial was moved to the end of the Maintenance Phase (Visit 4)
Section 5.2 Exclusion Criteria Section 8.3.3 Electrocardiograms	Exclusion criterion 13 modified to exclude subjects with QTcF values >450 msec, regardless of sex	Change made to be consistent with ICH E14
Section 5.4 Screen Failures	Text regarding rescreening was modified to indicate subjects would not retain their subject number in the event they were rescreened	Correction of inaccurate information
Section 6.7 Intervention after the End of the Trial	Modified text to indicate subjects who were eligible would enter Trial CVL-865-SZ- 002 after completion of the Maintenance Phase (Visit 4) of Trial CVL-865-SZ-001	In order to avoid unnecessary taper and re- titration of investigational medicinal product for subjects entering Trial CVL- 865-SZ-002, the point of entry into that trial was moved to the end of the Maintenance Phase (Visit 4)
Section 8.3.1 Physical and Neurological Examinations	Removed specifications on methods to measure height at screening	No standard method to measure height will be required
Section 8.3.2 Vital Sign Measurements	Added respiratory rate to list of vital signs to be measured; clarified vital signs would be measured with subject in sitting/semi-recumbent position; removed requirement for triplicate blood pressure and heart rate measurements; added specifications for measurement of body temperature	Further clarification on how to assess vital signs

Section # and Name	Description of Change	Brief Rationale
Section 8.3.3 Electrocardiograms	Added language stating clinically relevant changes in ECGs will be recorded in the AE section of eCRF	Inadvertent omission in original protocol
Section 8.6.3 Methods and Analysis	Added language to provide flexibility to use CVL-865 samples for future exploratory analyses for potential metabolites and method development activities	Judicious use of collected human samples for future use towards potential method development activities and understanding metabolic fate of CVL-865
Section 8.6.3 Methods and Analysis	Moved text regarding use of CVL-865 concentration data to Section 9.4.3 Other Analyses	Text was moved to a more appropriate location within protocol
Overall	Minor grammatical and wording corrections/clarifications made throughout protocol	Correct errors in original protocol

1. INTRODUCTION

This document describes the statistical methods and data presentations planned for the analysis of the efficacy and safety data from Protocol CVL-865-SZ-001. Background information is provided for the study designs and objectives. Further details of study conduct, and data collection are provided in the study protocol and electronic case report forms (eCRFs)

1.1. Study Overview

This is a double-blind, parallel-group, placebo-controlled trial with subjects randomized to 1 of the following 3 arms in a 1:1:1 ratio:

- CVL-865 25 mg BID maintenance
- CVL-865 7.5 mg BID maintenance
- Placebo

This maximum duration is to be approximately 25 weeks, consisting of the following:

- 8-week Screening/Baseline Period
- 10- or 13-week Treatment Period, including an initial 2-week Titration Phase, an 8-week Maintenance Phase, and a 3-week Taper Phase (only for subjects not continuing treatment in the open-label extension trial). The tablets (including the number of tablets given) will be the same between the placebo and both CVL-865 dose arms during the Titration, Maintenance, and Taper Phases to maintain the blind
- 4-week Follow-up Period (only for subjects not continuing treatment in the openlabel extension trial)

Subjects are to continue on their current AEDs at the same dosages throughout the Screening/Baseline Period. If a subject has a vagus nerve stimulator (VNS), a deep brain stimulator (DBS), or a responsive neurostimulator (RNS), the settings must remain stable throughout the Screening/Baseline Period.

During this Screening/Baseline Period, subjects will be required to complete electronic seizure diaries (eDiary) and record all seizures in the eDiary for each day and days free of seizures. The presence or absence of all seizure types experienced by each subject will be recorded daily in the eDiary.

Subjects who satisfy all inclusion/exclusion criteria and thus are eligible for the trial will be randomized to 1 of 3 treatment arms at Visit 1 (Day 1). The daily dosing schedule will start at Day 1 with a 2-week Titration Phase during which time the subject's dose will be increased in a blinded fashion up the randomized dose level (CVL-865 25 mg BID, CVL-865 7.5 mg BID, or placebo). In the high-dose group, CVL-865 will be administered as

during the Titration Phase, and then 25 mg BID during the 8-week Maintenance Phase. In the low-dose group, CVL-865 will be administered as

during the Titration Phase, and then

7.5 mg BID during the 8-week Maintenance Phase.

At the completion of the Maintenance Phase, the investigator will evaluate the subject's eligibility to continue treatment with CVL-865 in the open-label extension trial CVL-865-SZ-002. If the investigator determines the subject is eligible for the trial, he/she will discuss with the subject if they would like to continue into Trial CVL-865-SZ-002. If the investigator determines the subject agrees to continue participation in Trial CVL-865-SZ-002, consent will be obtained and unique procedures for Visit 1 of Trial CVL-865-SZ-002 will be completed.

For subjects who do not continue into Trial CVL-865-SZ-002, following the Maintenance Phase, the dose will be gradually decreased over a 3-week Taper Phase.

The trial design is depicted in Figure 1 and details of schedule of assessments are provided in Section 9.1.

[figure not shown]

Figure 1: Trial Schematic

Abbreviations: AED = anti-epileptic drug; BID = twice daily; OLE = open-label extension; Wk = week.

1.2. Sample Size Considerations

Approximately 214 subjects will be screened to achieve 150 subjects randomly assigned to treatment (50 per group) and 120 evaluable subjects for an estimated total of 40 evaluable subjects per treatment group.

A sample size of 50 subjects per group (total of 150 subjects) will provide at least 80% power to detect a difference in the means of the primary outcome measure (RRatio) of -20 (PASS 2008 Tests of Two Means, Two Sample T-Test, 2-sided alpha level = 0.1, Standard Deviation=34, and a 20% dropout rate). Approximately 214 subjects will be screened to achieve 150 subjects randomized.

In the event of higher than anticipated early terminations due to COVID-19 or other reasons, Cerevel may extend enrollment in order to maintain the planned statistical power.

1.3. Measures to Minimize Bias: Randomization and Blinding

1.3.1. Subject Assignment to Treatment

All subjects will be centrally randomized in a 1:1:1 ratio to 3 treatment arms (CVL-865 7.5 mg BID, 25 mg BID, or placebo) at the Visit 1 (Day 1) via an Interactive Voice Response System/Interactive Web Response System (IVRS/IWRS), according to a computer generated randomization scheme generated by a non-study statistician and be kept strictly confidential. Subjects will be sequentially assigned to the next available randomization number and will receive the IMP that corresponds to that randomization number. Once a randomization number has been assigned, it will not be reassigned.

1.3.2. Blinding

The CVL-865 and placebo tablets will be identical in appearance. Subjects will receive the appropriate combination of tablets necessary in order to achieve the required dose level. In order to maintain the blind, subjects assigned to the placebo treatment group will receive the same number of tablets as subjects in the CVL-865 groups.

Treatment assignments will be blinded to the investigators and other trial site personnel, the subjects, and all sponsor personnel who are involved in the conduct of the trial (including trial monitoring, data management, and data analysis). Access to the treatment codes will be restricted to personnel who are responsible for generating and maintaining the randomization code, packaging the IMPs, operating the IVRS/IWRS, analyzing the PK blood samples, or reporting serious adverse events (SAEs) or adverse events of special interest (AESI) to regulatory agencies.

If the investigator decides that unblinding is warranted, the investigator should make every effort to contact the medical monitor prior to unblinding a subject's treatment assignment unless this could delay emergency treatment of the subject. If a subject's treatment assignment is unblinded, the medical monitor must be notified within 24 hours after breaking the blind.

Documentation of breaking the blind should be recorded in the subject's medical record and eCRFs, with the reason for breaking the blind, the date and time the blind was broken, and the names of the personnel involved. Once the blind is broken for a subject, treatment with the IMP may not be reinitiated for that subject.

1.4. Treatment Period

The dose of CVL-865 will be titrated to the assigned dose over the first 2 weeks of the trial during the Dose Titration Phases followed by 8 weeks of Maintenance Phase at the assigned dose level. At the end of Maintenance Phase, eligible subjects have the option to continue treatment with CVL-865 in the open-label extension trial CVL-865-SZ-002. If for subjects who do not continue into Trial CVL-865-SZ-002, following the Maintenance Phase, the dose will be gradually decreased over a 3-week Taper Phase.

The dosing schedule is summarized in Table 1.

Table 1:	Dosing Schedule
----------	-----------------

	Titratio	n Phase	Maintenance Phase		Taper Pha	ise ^a
Dose Initiation			Day 15	Day 78	Day 85	Day 92
Duration	2 weeks		8 weeks		3 weeks	
CVL-865 7.5 mg BID			7.5 mg BID	5 mg BID	5 mg BID	2.5 mg BID
CVL-865 25 mg BID			25 mg BID	17.5 mg BID	10 mg BID	5 mg BID
Placebo	Placebo	Placebo	Placebo	Placebo	Placebo	Placebo

Abbreviations: BID = twice daily.

^a Only for subjects who do not continue treatment with CVL-865 in Trial CVL-865-SZ-002.

2. OBJECTIVES AND ENDPOINTS

The trial objectives and endpoints are summarized in Table 2.

Table 2:Objectives and Endpoints

Objectives	Endpoints	
Primary: To evaluate the efficacy of CVL-865 as adjunctive therapy compared with placebo in subjects with focal onset seizures	Primary Efficacy: RRatio, defined as RRatio=(T-B)/(T+B) ×100, where T represents the focal onset seizure frequency rate per week in the Maintenance Phase and B represents the focal onset seizure frequency rate per week in the Baseline Period	
	Key Secondary Efficacy:	
	Change from baseline in focal onset seizure frequency per week over the Maintenance Phase	
	• The 50% responder rate, defined as the percent of subjects with at least a 50% reduction in the Maintenance Phase focal onset seizure frequency rate relative to the Baseline Period	
	Other Secondary Efficacy:	
	Seizure freedom	
	Seizure rate over time	
	• PGIC score at Visits 2, 3, and 4	
	 Change from Baseline to Visits 2, 3, and 4 in CGI-S score 	
	• CGI-I score at Visit 2, 3, and 4	
	Change from Baseline to Visit 4 in QOLIE-31 Overall score	
	Change from Baseline to Visit 4 in HUI Utility score	
Secondary (safety): To evaluate the safety and tolerability of CVL-865 in subjects with focal onset seizures	 Treatment-emergent adverse events, clinically significant changes in ECGs, vital sign measurements, and physical and neurological examination results 	
	 Suicidality assessed using the C-SSRS 	
	 Withdrawal symptoms assessed using the mCIWA-B 	
	 Nature, frequency, and temporality of TEAEs (nonserious and serious), including abuse- related AEs and AEs related to Medication Handling Irregularities (MHI) 	

Objectives	Endpoints
Secondary (PK): To evaluate the plasma exposure of CVL-865	• Summary listing of CVL-865 concentrations by dose and visit

Abbreviations: AE = adverse event; CGI-I = Clinical Global Impression – Improvement; CGI-S = Clinical Global Impression – Severity of Symptoms; C-SSRS = Columbia-Suicide Severity Rating Scale; ECG = electrocardiogram; HUI = Health Utilities Index; mCIWA-B = Modified Clinical Institute Withdrawal Assessment – Benzodiazepines; MHI = Medication Handling Irregularities; PGIC = Patient's Global Impression of Change; QOLIE-31 = Quality of Life in Epilepsy-31; RRatio = Response Ratio; TEAE = treatment-emergent adverse event.

3. **KEY ASSESSMENTS AND DERIVATIONS**

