15.	Subjects with other abnormal laboratory test results, vital sign results, or ECG findings unless, based on the investigator's judgment, the findings are not medically significant and would not impact the safety of the subjects or the interpretation of the trial results. The medical monitor should be contacted to discuss individual cases, as needed.									
	Tests with exclusionary results should be repeated to ensure reproducibility of the abnormality before excluding a subject based on criteria provided in this protocol. For ECGs, 3 consecutive recordings are required and if 2 of the 3 remain exclusionary, then the subject is not eligible for the trial.									
Disallow	ed Prior and Concomitant Medications									
16.	Subjects receiving more than 3 background AEDs for their epilepsy.									
17.	Subjects taking BZD medication chronically or who require a BZD (oral, intramuscular, or suppository) as rescue medication for epilepsy for more than 4 days on average over a 28-day period. (Note: a rescue BZD will be permitted if used ≤4 days on average over a 28-day period). During the Screening/Baseline Period, subjects requiring a BZD (oral, intramuscular, or suppository) as rescue medication for epilepsy more than 4 days on average over a 28-day period will be excluded.									

18.	Subjects taking other prohibited medications prior to randomization (as listed in Table 6) or who would be likely to require the use of prohibited concomitant medications during the trial (as listed in Table 7).
19.	Subjects taking any drug that is strong or moderate inducer/inhibitor CYP3A4 metabolism, which has the potential to alter CVL-865 exposure levels (see Section 6.5).
20.	Subjects taking any drug that is a sensitive P-gp and BCRP substrate (see Section 6.5).
21.	Vigabatrin is excluded as a concomitant AED, unless subject has been taking it for at least 2 years prior to signing the ICF and have no evidence of visual field defects on at least 2 visual field tests within 6 months of signing the ICF.
22.	Felbamate is excluded as a concomitant AED, unless subject has been taking it for at least 2 years prior to signing the ICF, with a stable dose for $\geq$ 49 days, and have acceptable hematology and liver function test values (or discontinued felbamate no less than 49 days prior to signing the ICF).
Other	
23.	Female subjects who are breastfeeding and/or who have a positive pregnancy test result prior to receiving IMP.

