4.1.6. Baseline Value

For purposes of analysis of safety assessments and efficacy assessments outside of eDiary, the baseline value is defined as the last value obtained prior to initiation of IMP. Should the Day 1 visit value be obtained after the first dose of IMP or if this value is not available at Day 1, then the most recent value obtained prior to earliest initiation of IMP will be used for the baseline value.

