5.14.3. Clinical Laboratory Assessments

Descriptive summaries of selected (quantitative) clinical laboratory results will be presented by treatment group and study visit. Laboratory values outside the normal range for each systematically collected hematology, blood chemistry, and urinalysis parameter will be identified. Each subject's hematology, blood chemistry, and quantitative urinalysis values will be flagged as "low" (below the lower limit of normal/LLN), "normal" (within the normal range), or "high" (above the upper limit of normal/ULN) relative to the normal ranges of the central laboratory. Each subject's qualitative urinalysis results will be flagged as "normal" or "abnormal." In addition, the severity of laboratory abnormality will be graded based on toxicity criteria specified in Section 9.6 in reference to Common Terminology Criteria for Adverse

Events (CTCAE) Version 5.0. The result of each laboratory test for individual subjects will be presented in a listing with the normal range defined by the central laboratory, the status relative to the normal range, and the toxicity grade.

Shift table will be used to summarize shifts from baseline toxicity grades to greatest (worst) treatment-emergent laboratory toxicity. For hematology and, blood chemistry, and quantitative urinalysis parameters that toxicity grade was not defined, a shift table for each laboratory test will be based on the shift from baseline high/normal/low status to the status of the maximum post-baseline value and the minimum post-baseline value (including test results from unscheduled visits, if any). Similarly, for qualitative urinalysis parameters, shifts from baseline normal/abnormal status to the worst post-baseline status will be summarized.

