5.14.4. Vital Signs

Vital sign measurements will include body temperature (oral or tympanic), respiratory rate, body weight, systolic blood pressure, diastolic blood pressure, and heart rate. Body temperature, blood pressures, and heart rate will be measured with the subject in a sitting/semi-recumbent position after a 5-minute rest. For the body temperature, the same method must be used for all measurements for each individual subject and should be the same for all subjects at each

investigational site. Vital signs and corresponding changes from baseline will be summarized by visit and treatment group using descriptive statistics.

Number and percent of subjects with out-of-range post-baseline vital signs will be summarized based on the following criteria:

- Systolic Blood Pressure
 - < 90 mmHg,
 - >140 mmHg
- Diastolic Blood Pressure
 - < 50 mmHg
 - > 90 mmHg
- Heart Rate (Supine)
 - < 60 bpm
 - >100 bpm
- Respiratory Rate
 - <12 bpm
 - > 20 bpm
- Temperature
 - $< 36^{\circ} C$
 - $> 38^{\circ} C$

Vital signs results will also be presented as listing with the out-of-range value flagged based on the above criteria.

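### The only categorical vital-sign table in SAP 5.14.4 ignores baseline, so it mixes pre-existing with new abnormality and dilutes a difference between arms in that table

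*SAP*

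**What the plan says.** SAP Table 2 lists among the secondary safety endpoints "clinically significant changes in ECGs, vital sign measurements, and physical and neurological examination results". Neither document defines a clinically significant change in a vital sign by size.

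SAP 5.14.4 plans three outputs:

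- A continuous summary: "Vital signs and corresponding changes from baseline will be summarized by visit and treatment group using descriptive statistics".
- A categorical table: "Number and percent of subjects with out-of-range post-baseline vital signs will be summarized based on the following criteria". The limits are absolute, for example systolic pressure <90 or >140 mmHg, diastolic <50 or >90 mmHg, heart rate <60 or >100 bpm. The subject's baseline plays no part.
- A listing: "Vital signs results will also be presented as listing with the out-of-range value flagged based on the above criteria".

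Protocol 5.2, exclusion 15, does not require in-range vital signs at entry. It excludes subjects with abnormal "vital sign results, or ECG findings unless, based on the investigator's judgment, the findings are not medically significant". Ages run to 75.

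The SAP has what it needs to refer to baseline. In Section 4.1.6 "the baseline value is defined as the last value obtained prior to initiation of IMP". For laboratory data, 5.14.3 says: "Shift table will be used to summarize shifts from baseline toxicity grades to greatest (worst) treatment-emergent laboratory toxicity". For QTcF, 5.14.5 tabulates increases from baseline beside the absolute categories.

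SAP 5.14.4 also labels the heart-rate limits *Supine*, while the same section and Protocol 8.3.2 have heart rate measured sitting or semi-recumbent.

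**The concern.** The endpoint is about change, but the one table that counts subjects is about level. Someone with a systolic pressure of 145 before dosing and 143 afterwards is counted, although nothing has worsened. Such subjects add similar counts to every arm, so a real difference in new abnormality looks smaller, in absolute and especially in relative terms. With about 50 subjects per arm, a chance imbalance in baseline abnormality can also move the table in either direction.

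A categorical table exists to show individual subjects who move into an abnormal range. As planned, it cannot separate them from those who were there already. Laboratory tests and QTcF, which also get categorical tables, each have one that refers to baseline; vital signs have none.

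**Working it through.** **Inputs from the documents.** 50 randomized per arm (SAP 1.2), allocation 1:1:1, safety set = all randomized and dosed (SAP 5.2). Vital signs are scheduled after baseline at Visits 3, 4 and 5, so at most three scheduled readings; subjects entering the extension after Visit 4 have two. The plan states no vital-sign rate or precision, so there is no figure to reproduce.

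**Inputs assumed.** Let b = share beyond the limit at baseline, r = chance that such a subject is beyond it again afterwards, p = rate of newly crossing the limit among the rest.

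**Formulas.**

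- Planned count in an arm: P = b·r + (1−b)·p.
- Share of counted subjects already out of range: b·r / P.
- If b and r are equal in both arms, the planned difference is (1−b) times the new-onset difference.
- z = difference / √[Σ p(1−p)/n], with n = 50 for the planned table and n = 50(1−b) for new onset only.

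**Values for b, r and p.** These come from simulating normal readings with a between-subject and a within-subject SD, three post-baseline visits and no drug effect. A 10-point new-onset difference is then added in the active arm.

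| Limit and assumed distribution (mean; between SD; within SD) | b | r | p, no drug effect | Already out of range, of those counted | z, planned table | z, new onset only |
|---|---|---|---|---|---|---|
| SBP >140 (124; 13; 8) | 15% | 0.78 | 17% | 45% | 0.93 | 1.13 |
| HR <60 (72; 9; 6) | 13% | 0.75 | 17% | 41% | 0.96 | 1.14 |
| SBP >140 (116; 12; 8) | 5% | 0.64 | 7% | 31% | 1.36 | 1.51 |

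First row by hand, with rounded inputs:

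- Placebo: 0.15×0.78 + 0.85×0.17 = 0.117 + 0.1445 = 0.2615.
- Active: 0.117 + 0.85×0.27 = 0.3465.
- Difference 0.085, which is 0.85×0.10.
- Already out of range, placebo: 0.117/0.2615 = 45%.
- z planned: 0.085 / √[(0.2615×0.7385 + 0.3465×0.6535)/50] = 0.085/0.0916 = 0.93.
- z new onset: n = 42.5; 0.10 / √[(0.17×0.83 + 0.27×0.73)/42.5] = 0.10/0.0892 = 1.12 (1.13 unrounded).

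**Sensitivity to p.** If new onset without drug effect were rare, the loss would be larger. With b = 20%, r = 0.8 and 5% vs 15%, the planned table shows 20% vs 28% (z = 0.94), against z = 1.51 for new onset only. At b = 10% the pair is 1.21 and 1.60; at b = 30%, 0.76 and 1.41.

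**Chance imbalance.** The SD of the between-arm difference in b is √[2b(1−b)/50]: 6 points at b = 10%, 8 at 20%, 9 at 30%.

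The z values only show how visible a difference would be; no test of vital signs is planned.

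**The case against.** The strongest reply is that the endpoint has another route. Protocol Appendix 3, Table 11, makes a vital-sign abnormality that the investigator considers clinically significant an adverse event, including one that worsens from baseline. Events from first dose onward are treatment-emergent (SAP 3.2.1.1) and tabulated by arm (5.14.1). This stands. A reader might infer from 5.14.4 that the stated endpoint goes unmeasured; the documents do not support that.

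Nor do the continuous summaries hide extremes. SAP 5.1 defines descriptive statistics to include quartiles, minimum and maximum, so the largest rise and fall per arm and visit will be shown, and the listing shows individual values.

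The SAP also uses absolute limits without a baseline condition for worst QTcF and for liver multiples. That is true, but QTcF has increase categories beside them, and liver tests fall under the laboratory shift tables. Vital signs have no such companion.

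A reader might take the pair 0.94 and 1.51 as the size of the loss. It requires 5% new onset on placebo with 20% out of range at baseline. Under the variability assumed above, about 17% cross the limit newly with no drug effect when about 15% are out of range at baseline. Most of the noise is within-subject variation, which a new-onset count keeps.

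Finally, it may be tempting to say that many subjects start out of range. The documents do not show this: exclusion 15 admits only findings judged not medically significant, and exclusion 7 removes significant cardiovascular disease. If nobody is out of range at baseline, the dilution is zero.

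**Conclusion.** The point holds, with limited reach. The one categorical vital-sign table does not separate abnormality present before dosing from abnormality that appears afterwards, and entry rules allow the former. Under assumed baseline shares of 5% to 15%, about 30% to 45% of counted subjects were already out of range. Conditioning on baseline then adds roughly 0.15 to 0.20 to z for a 10-point difference at 50 per arm. These sizes rest on assumed distributions, equal b and r in the arms, and three post-baseline readings.

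One might read this as a plan that would conceal a drug effect on vital signs. That goes too far: the change summaries and the adverse event tables are untouched, and Protocol 4.3 reports no vital-sign changes at doses up to 100 mg. This is a descriptive secondary safety output in a trial the SAP calls exploratory. Priority is low.

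The *Supine* label is a separate inconsistency that needs no assumption and changes no count.

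**What to change.** In SAP 5.14.4, keep the existing table and add one of the following:

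- for each vital sign with limits, a low/normal/high shift from baseline to the maximum and to the minimum post-baseline value, on the pattern of 5.14.3; or
- for each limit, the number of subjects who cross it after baseline among those not beyond it at baseline, with that number as denominator.

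The existing table should stay. A new-onset count drops subjects already beyond a limit, and a low/normal/high shift does not register further worsening within the same category. Neither addition measures size of change, so the change-from-baseline summaries remain necessary.

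Reconcile the *Supine* heart-rate label in 5.14.4 with the sitting or semi-recumbent position stated there and in Protocol 8.3.2.

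Cost: SAP wording and one extra table, with no new data. The new-onset denominator is slightly smaller, for example 42.5 instead of 50 per arm on average at b = 15%.
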